2.7 Treatment Procedures

- The defined study area will be identified and may be marked with a white or yellow, washable marker.
- A topical anesthetic may be applied to the treatment area prior to treatment.

- To avoid eye injury, appropriate eye protection for the wavelength being used must be worn by all individuals in the room during treatment.
- Test spots should be performed prior to each treatment.
- The Skintel Melanin Reader will be used for objective measurement of the melanin content of skin. The Skintel Reader will provide guidance to help select test spot settings.
- Procedures for the Elite iQ treatment:
 - o The device will be used in accordance with the Operator's Manual.
 - Pulses will be delivered in a linear fashion with no more than a 10% overlap between pulses.
 - An air-cooling system may be used during treatment. The air-cooling system allows for the continuous flow of cold air on the treatment area to ease the sensation from the laser pulse.
 - A thin coating of gel, aqueous or surgical lubricant, clear aloe, clear ultrasonic gel, or water can be used in conjunction with the system as a conduit for the laser energy and to increase cooling efficiency of the treatment site.
 - Parameters may be adjusted throughout the treatment in order to increase subject comfort.
 - O Subjects will be asked to report the general level of treatment discomfort/pain on a scale of 0 (none) to 10 (maximum intolerable pain).
 - o Parameters and skin reaction will be continuously monitored and recorded during treatment.
- The additional treatments will follow the same procedure.
- Subjects may receive between 1-5 treatments on each treatment area. Subjects may return for a treatment visit every 2-10 weeks.

2.8 Post Treatment Procedures

- Adverse events will be documented after treatment.
- Following treatment, an aloe-based gel, chiller, and/or cold pack may be applied to soothe the skin.
- Photographs may be taken post treatment.
- The following post treatment instructions will be reviewed with subject:
 - Wash the treatment area gently with soap and water. Do not soak. Gently pat area to dry.
 - o Following treatment, apply an aloe-based gel or equivalent (such as a cold pack) to soothe and moisturize the skin.
 - o Do not shave the treated area if blistering or crusting is evident.
 - o Avoid contact sports or any other activity that could cause bruising of the treated area.
 - o Following the laser treatment, activities, such as swimming, sports, or strenuous exercise should be avoided for the first 2–3 days, or until any redness, crusting, or blisters have resolved.
 - o For vein treatment, avoid exercises that can cause vasodilatation for 1-week posttreatment. Walking is encouraged after vein treatment.
 - Avoid sun exposure throughout the course of treatment and use a broad-spectrum (UVA/UVB) sun block SPF 30 or greater when treatment area is exposed to the sun.

- Avoid sun exposure as delayed secondary blistering has been noted up to 72 hours posttreatment.
- Contact physician if there is any sign of blistering or infection (redness, tenderness, or pus).
- o An antibiotic cream should be used if there is any blistering or break in the skin.
- o Do not use tanning beds.
- o Avoid hot baths/whirlpools for 1 week following treatment (vein treatment).
- Normal skin care regimens, i.e., makeup, moisturizers, deodorant, and shaving may be resumed the day after treatment if there is no redness, blistering, or crusting present. If makeup is allowed, apply and remove it delicately. Excess rubbing can open the area and increase the chance of scarring. If the area blisters, extreme caution should be used when applying or removing makeup. The treated area is very delicate and should be treated with care.
- o For vein treatment, discomfort, such as swelling or redness (lasting from a few hours to a couple of days), can be relieved with acetaminophen (such as Tylenol) or ice packs.
- Apply lotion to the area to prevent drying and crusting. Lotion applied following the laser treatment can have a soothing effect. If a crust develops, allow it to fall off naturally. Do not scratch or pick (vein treatment).
- o Treated pigmented lesions will likely crust then slough over the course of several days or weeks. Do not scratch or pick at crusts.

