1.2 Objectives

- 1. Primary Objectives:
 - To assess the safety of the study devices through the collection of side effects throughout the study.
 - To assess efficacy by blinded evaluation of photography.
- 2. Secondary Objectives:
 - To assess of efficacy of the study device through Investigator and subject questionnaires.
 - To assess the ease of use of the new device.

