2.9 Follow Up

- The study subjects are required to return to Investigator site for a follow up evaluation between 30 90 days post last treatment.
- Subject and Investigator questionnaires may be performed at these visits.
- Photographs will be taken, and adverse events will be documented at all follow up visits.
- Some subjects may have an incomplete response or no response by the end of the study. At the end of the study, treatments using an FDA approved/cleared treatment method may be discussed with the subject and obtained at the cost of the subject.

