2.12 Schedule of Visits and Procedures

	Visit #1*	Visit #2-6	Visit #7
Procedure	Screening and Pretreatment Procedures	Treatment Visit(s) #1 (required) #2-5 (optional) (2 – 10 Weeks Apart)	Follow Up 60 Days Post Last Tx (+/- 30 Days)
Medical History	X		
Pregnancy Verification	X		
Informed Consent	X		
Photographs	X	X	X
Treatment		X	
Treatment Discomfort/ Pain Evaluation		X	
Subject Questionnaires			X
Investigator Questionnaire			X
Adverse Events Assessment		X	X

^{*}Screening and Pretreatment Procedures may occur at the same time as the first Treatment Visit.

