2.14 Adverse Event Recording

All data captured must be supported by the Investigator's timely assessment and documentation of the adverse event in the case report forms or source documents. All documented adverse events will be reviewed by the Sponsor or designee to determine whether the adverse event meets regulatory reporting requirements and to ensure timely adverse event reporting to meet local and global regulatory requirements. All adverse events must be followed until their resolution.

Adverse Events Pertaining to the Elite iQ Device:

- Subjects may experience some temporary erythema, edema, bruising, or irritation of the skin around the treatment site.
- Scarring, though rare, can occur following any laser procedure.
- Blistering during treatment may be an indication of sun exposure or an excessive fluence setting for the skin type. Blistering can occur during the first three days following the laser procedure.
- Other acute changes may include scaling or scabbing. These changes are often associated with higher energies and their incidence decrease when treatment energies are reduced.
- Histamine/Hives: some subjects may develop raised papules similar to hives. This irritation usually subsides in a few hours.
- Pustules, pimples, or folliculitis may develop in the first few days following treatment.
- Hyperpigmentation or hypopigmentation can occur following the laser treatment. Pigmentary changes have been reported to be transient although they may last for several months or longer.
- Hemosiderin Staining- The treated vessel may leak tiny amounts blood into the tissue. When the red blood cells die, iron released from the hemoglobin is converted into hemosiderin and stored in the tissue beneath the skin. This shows up as a brown/purple stain on the skin. It usually will fade over time, but some may require further treatment to resolve.

Adverse Events Pertaining to Gel:

The gel is a water-based gel that may be placed on the skin during the Elite iQ treatment. No known adverse events are documented. However, an allergic reaction is always possible when placing a topical gel onto the skin. Allergic reaction may include a mild reaction such as skin redness, irritation or hives.

Adverse Events Pertaining to Anesthesia:

Topical anesthesia, such as but not limited to; EMLA, LMX and Lidocaine/Tetracaine, will be used. The most common side effects for most anesthetics include redness, blanching, swelling and application site reaction.

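### No scheduled adverse event contact covers the first 72 hours after a subject leaves the site, so counts of mild, short-lived reactions that start after discharge depend on spontaneous report and recall and may be too low

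*Combined protocol and SAP*

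**What the plan says.** The first primary objective in section 1.2 is "To assess the safety of the study devices through the collection of side effects throughout the study". Section 2.15.1 makes study success depend on two things: that treatment parameters are developed, and that the physician finds the side effects acceptable. Section 2.15.6 summarises adverse events as numbers and percentages, with no statistical comparison.

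Scheduled observation is as follows.

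- During a session (2.7): "Parameters and skin reaction will be continuously monitored and recorded during treatment".
- After a session (2.8): "Adverse events will be documented after treatment". No time point or later contact is given.
- Next session (2.7): "Subjects may return for a treatment visit every 2-10 weeks".
- Visit 7 (column heading in 2.12): "Follow Up 60 Days Post Last Tx (+/- 30 Days"). Section 2.9 adds: "Photographs will be taken, and adverse events will be documented at all follow up visits".

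The protocol also says when reactions are expected. Section 2.8 warns that "delayed secondary blistering has been noted up to 72 hours posttreatment", and section 2.14 says "Blistering can occur during the first three days following the laser procedure". Section 2.14 places pustules, pimples and folliculitis in the first few days, and says that hives usually settle within hours.

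Four provisions apply between visits. Section 14.0 requires every adverse event from the first treatment onward to be recorded, and says that capture runs throughout the study. It also lets subjects contact the investigator whenever they wish. Section 2.8 tells them to contact the physician about blistering or signs of infection. Sections 2.1 and 2.10 allow an unscheduled visit (2.1 also a phone call) at the subject's request or the investigator's judgement.

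**The concern.** The protocol expects some reactions to appear in the hours and days after the subject goes home, and no scheduled assessment falls in that period. A mild reaction that starts after discharge and clears before the next visit enters the data only if the subject reports it unprompted or remembers it weeks later.

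This bears on a primary outcome. An event that is never reported can only lower the count, so the error, if there is one, runs towards an acceptable side effect profile. It also touches the other half of the success rule. Section 2.14 links blistering during treatment to sun exposure or an excessive fluence setting, and scaling or scabbing to higher energies. Reactions that are lost, or credited to the wrong session, make it harder to relate settings to side effects.

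**Working it through.** The plan states no figure on this point. The 20 subjects in 2.15.2 have no event rate, precision target or power behind them, so there is nothing to reproduce. The check is of timing.

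**Step 1. Time to the next scheduled assessment.** Day 0 is the session.

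- Next treatment visit: 2 to 10 weeks × 7 = day 14 to day 70.
- Visit 7: 60 − 30 = day 30 to 60 + 30 = day 90 after the last treatment.

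**Step 2. Distance from the expected delayed-reaction period.** 72 hours = 3 days (2.8 and 2.14 agree).

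| Next scheduled assessment | Earliest | Latest | Days after the 72-hour period ends |
|---|---|---|---|
| Next treatment visit | day 14 | day 70 | 14 − 3 = 11 to 70 − 3 = 67 |
| Visit 7 | day 30 | day 90 | 30 − 3 = 27 to 90 − 3 = 87 |

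No permitted timing puts a scheduled assessment inside the period once the subject has left.

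**Step 3. Which reactions are exposed.** The reactions in 2.14 fall into three groups.

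- Immediate ones, such as erythema and edema, can be seen during or just after the session. Hives have no stated onset and may also be seen on site.
- Lasting ones may still be visible at a later visit. Section 2.14 says pigment change can last months, and section 2.8 says crusting of treated pigmented lesions can take days or weeks to clear.
- Mild ones that start after discharge and clear within days are the exposed group: pustules, pimples, folliculitis and small blisters.

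**Step 4. Whether the plan collects these actively.** Section 14.0 says what must be recorded but not how staff learn of it. Unscheduled contact is optional. The instruction to call covers blistering and infection, not the rest of the 2.14 list. The same instructions describe home care for blistering, so a subject may treat a mild reaction as routine. The text contains no diary, early call or required question about the interval since the last session.

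**Step 5. Effect on the reported figure.** If a reaction truly occurs in a share p of n subjects and a share c of affected subjects is captured, the expected count is n × p × c and the expected shortfall is n × p × (1 − c). With n = 20, each affected subject missed lowers the percentage by 1/20 = 5 points, and by more if fewer than 20 are treated. The documents give neither p nor c. If c = 1 there is no under-count.

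**The case against.** The best case for the plan is that recording is not tied to visits. All events from the first treatment must be recorded, subjects are told to call about blistering or infection, and unscheduled contact is available. Immediate and lasting reactions can be seen at scheduled visits. The case report form and the pre and post treatment instructions (Attachments V and IV) were not available for review, and the form may already ask for onset dates or events since the last session. The study is a small, open-label, descriptive study of a cleared device.

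Much of this stands. It narrows the exposed group to mild, short-lived reactions that begin at home, and it limits confidence in what the site will actually ask. Blisters are better protected than other reactions because subjects are told to report them. It does not close the gap, because an intent to record everything is not a method for learning of unreported events.

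Two stronger readings are tempting, and the documents support neither. A reader might infer that the primary safety result will under-count these reactions. The text shows only a risk, since complete reporting and recall would leave no loss. A reader might also infer that a reaction to one session is asked about only after the next has been delivered, because 2.6 lists no adverse event review and 2.8 places documentation after treatment. But the schedule in 2.12 marks adverse event assessment for the treatment visit as a whole and sets no order within it. What can be said is that the order and any look-back question are unspecified.

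**Conclusion.** The point holds in limited form. No scheduled adverse event contact falls in the first 72 hours after discharge, and the next one is 14 to 70 or 30 to 90 days after the session. Counts of mild, short-lived reactions with onset at home therefore depend on spontaneous report and recall. They may be too low, in the direction that favours success.

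The timing follows directly from the protocol. The size of any under-count cannot be computed from it, and a figure built on assumed reaction and capture rates would not be evidence about this study. The conclusion assumes that the unseen case report form and subject instructions add no active solicitation, so confidence is moderate. The change is worth making because it is cheap and protects a primary outcome.

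**What to change.** - **Sections 2.8 and 2.12:** after every session, give each subject a one-page day 0-7 checklist of the section 2.14 reactions, with onset date, end date and severity, to be returned at the next visit. Add it to the schedule. This is the part that covers the first 72 hours.
- **Sections 2.6 and 2.9:** add a solicited question about reactions since the last session, asked before the next treatment and at Visit 7. Record which session each event followed. This question alone would still rely on recall over weeks, so it supplements the checklist and does not replace it.

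If the case report form already contains the look-back question, the protocol need only refer to it.

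These changes affect data collection only. They add no visit or staff and alter no treatment rule. The costs are a small burden on subjects, an amendment with the written IRB approval that section 21.0 requires, and side-effect figures that will probably look less favourable.

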2.9 Follow Up

- The study subjects are required to return to Investigator site for a follow up evaluation between 30 90 days post last treatment.
- Subject and Investigator questionnaires may be performed at these visits.
- Photographs will be taken, and adverse events will be documented at all follow up visits.
- Some subjects may have an incomplete response or no response by the end of the study. At the end of the study, treatments using an FDA approved/cleared treatment method may be discussed with the subject and obtained at the cost of the subject.

2.10 Unscheduled Visits

An unscheduled visit may be performed at any time during the study at the subject's request or as deemed necessary by the site Investigator. The date and reason for the unscheduled visit will be recorded in the source documentation.

2.11 Replacement of Subjects

Replacement of subjects who have withdrawn or been withdrawn from the study will be allowed to be replaced with prior approval from the sponsor and/or IRB.

2.12 Schedule of Visits and Procedures

	Visit #1*	Visit #2-6	Visit #7
Procedure	Screening and Pretreatment Procedures	Treatment Visit(s) #1 (required) #2-5 (optional) (2 – 10 Weeks Apart)	Follow Up 60 Days Post Last Tx (+/- 30 Days)
Medical History	X		
Pregnancy Verification	X		
Informed Consent	X		
Photographs	X	X	X
Treatment		X	
Treatment Discomfort/ Pain Evaluation		X	
Subject Questionnaires			X
Investigator Questionnaire			X
Adverse Events Assessment		X	X

^{*}Screening and Pretreatment Procedures may occur at the same time as the first Treatment Visit.

2.13 Evaluation Methods

Photographs:

Photographs will be taken at all visits and will be used to assess safety and efficacy of treatment.

Treatment Discomfort/Pain Evaluation:

Subjects will be asked to report the general level of treatment discomfort on a scale of 0 (none) to 10 (maximum intolerable pain) using the universal pain assessment tool (Appendix B)

Subject Questionnaire:

The subject will be asked their level of satisfaction using a 6-point Likert scale that ranges from "extremely satisfied" to "extremely unsatisfied."

Subject Satisfaction		
Rating	Description	
6	Extremely Satisfied	
5	Satisfied	
4	Slightly Satisfied	
3	Slightly Unsatisfied	
2	Dissatisfied	
1	Extremely Unsatisfied	

Physician Questionnaire:

The Clinical Global Aesthetic Improvement Scale (CGAIS) ranging from "worse" to "very much improved" will be used to judge the improvement as seen by the treating Investigator.

Global Aesthetic Improvement Scale Assessment		
Rating	Description	
1	Very Much Improved- Optimal cosmetic result in this subject	
2	Much Improved- Marked improvement in appearance form the initial	
condition, but not completely optimal for this subject.		
3	Improved- Obvious improvement in appearance from initial condition, but a re-treatment is indicated.	
4	No Change- The appearance is essentially the same as the original condition.	
5	Worse- The appearance is worse than the original condition.	

2.14 Adverse Event Recording

All data captured must be supported by the Investigator's timely assessment and documentation of the adverse event in the case report forms or source documents. All documented adverse events will be reviewed by the Sponsor or designee to determine whether the adverse event meets regulatory reporting requirements and to ensure timely adverse event reporting to meet local and global regulatory requirements. All adverse events must be followed until their resolution.

Adverse Events Pertaining to the Elite iQ Device:

- Subjects may experience some temporary erythema, edema, bruising, or irritation of the skin around the treatment site.
- Scarring, though rare, can occur following any laser procedure.
- Blistering during treatment may be an indication of sun exposure or an excessive fluence setting for the skin type. Blistering can occur during the first three days following the laser procedure.
- Other acute changes may include scaling or scabbing. These changes are often associated with higher energies and their incidence decrease when treatment energies are reduced.
- Histamine/Hives: some subjects may develop raised papules similar to hives. This irritation usually subsides in a few hours.
- Pustules, pimples, or folliculitis may develop in the first few days following treatment.
- Hyperpigmentation or hypopigmentation can occur following the laser treatment. Pigmentary changes have been reported to be transient although they may last for several months or longer.
- Hemosiderin Staining- The treated vessel may leak tiny amounts blood into the tissue. When the red blood cells die, iron released from the hemoglobin is converted into hemosiderin and stored in the tissue beneath the skin. This shows up as a brown/purple stain on the skin. It usually will fade over time, but some may require further treatment to resolve.

Adverse Events Pertaining to Gel:

The gel is a water-based gel that may be placed on the skin during the Elite iQ treatment. No known adverse events are documented. However, an allergic reaction is always possible when placing a topical gel onto the skin. Allergic reaction may include a mild reaction such as skin redness, irritation or hives.

Adverse Events Pertaining to Anesthesia:

Topical anesthesia, such as but not limited to; EMLA, LMX and Lidocaine/Tetracaine, will be used. The most common side effects for most anesthetics include redness, blanching, swelling and application site reaction.

Less common side effects include large swellings that look like hives on the skin or in the mouth or throat, pain, burning, paleness and altered temperature sensation. Subjects may be allergic to the contents of any anesthetic which may cause allergic-type reactions including anaphylactic symptoms and life-threatening or less severe asthmatic episodes in certain susceptible people.

Adverse Events Pertaining to the Marker:

Using surgical marker has minimal risks and may produce effects on the body such as redness or a rash.

Other Cautions:

Incomplete response or no response may occur since some subjects may not respond to treatment.

2.15 Statistical Analysis

2.15.1 Hypothesis

For this study to be considered a success, parameters are developed, and the side effect profile is acceptable to the Physician as it relates to this type of treatment.

For secondary objectives to be considered a success, the results from any assessments will need to be statistically significant or have $\geq 80\%$ response rate. In cases where the subject's improvement is being graded on a scale, such as the GAIS scale, we will test the statistical significance of our results against a hypothetical population that would have no change (average score of 4).

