2.15.4 Analysis of Demographic and Medical History Variables

Summaries will be prepared for all important demographic and medical history variables. For quantitative variables summaries will include the sample size, mean, median, standard deviation, minimum, and maximum. For these variables the treatment groups will be compared using either a t-test or a Wilcoxon Rank Sum test, as appropriate. For categorical variables the summaries will include the sample size and the number and percent of patients for each outcome. For these variables the treatment groups will be compared using Fisher's Exact test. Statistical significance will be declared if the two-sided p-value is < 0.05.

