2.15.5 Analysis of Efficacy Variables

The primary efficacy variable is the change from baseline to visit 7 (60 days post last treatment, +/- 30 days) with respect to the indication being treated as evaluated by physician grading with CGAIS. Baseline is defined as the last assessment prior to the first treatment. The change from baseline to visit 13 will be analyzed using a Mixed Model Repeated Measures Analysis of Variance. A pairwise treatment group comparison at visit 7 will be performed using the results of this analysis. If a patient has no post-baseline assessment of the primary efficacy variable the patient data will be excluded from the statistical analysis of the improvement. Statistical

significance with respect to the treatment group comparison at visit 7 will be declared if the two-sided p-value is < 0.05. For each treatment group summaries will be prepared for both the observed assessment and the change from baseline. Subject satisfaction results from Visits 12 and 13 will also be included in the summary. The summaries will include the sample size, mean, median, standard deviation, minimum, and maximum. Categorical variables will also include a summary which will include the number and percent of patients for each outcome. The statistical significance of the mean change from baseline for each treatment group will be determined using a student's paired t-test.

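### Section 2.15.1 does not say which secondary assessment decides success, by which route or in which direction; if one of two or three tests suffices, the false-positive chance is about 1.6 to 2.9 times that of a single test

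*Combined protocol and SAP*

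**What the plan says.** Section 1.2 lists two secondary objectives: "To assess of efficacy of the study device through Investigator and subject questionnaires" and "To assess the ease of use of the new device". Section 2.13 supplies a five-grade CGAIS for the investigator and a six-point satisfaction scale for the subject. Neither 2.12 nor 2.13 gives an instrument or a time point for ease of use.

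Section 2.15.1 sets the success rule for these objectives: "the results from any assessments will need to be statistically significant or have" a response rate of 80% or more. For scales that grade improvement, such as the GAIS, significance is to be tested "against a hypothetical population that would have no change (average score of 4"). No other null value is given, and response is not defined for any scale.

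The rule itself carries no significance level. The level appears in 2.15.4 ("Statistical significance will be declared if the two-sided p-value is < 0.05") and in 2.15.5 ("significance with respect to the treatment group comparison at visit 7 will be declared if the two-sided p-value is < 0.05"). Both places concern comparisons between treatment groups, although 2.2 describes an open-label study at one center with no comparator.

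Sections 2.15.3 to 2.15.6 contain no order of testing, no adjustment for multiple tests and no exploratory label for secondary results. Section 2.15.5 does single out one variable, graded by CGAIS: "The primary efficacy variable is the change from baseline to visit 7".

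**The concern.** The rule attaches a formal verdict to a family of assessments without saying how the family is combined. *Any assessments* can mean that one passing result is enough, or that each assessment made must pass. Each assessment also has two ways to pass, and no direction is stated.

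If the investigator's grades show no improvement but subjects report satisfaction, or the reverse, the two readings give opposite verdicts. The sponsor could then claim secondary efficacy success on whichever questionnaire and whichever route came out well, and present it as a 5% test. This matters because it is the only efficacy success rule in 2.15.1; the overall criterion there concerns parameters and side effects.

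**Working it through.** **Inputs from the documents.** The level is two-sided 0.05 (2.15.4, 2.15.5). The sample is 20 subjects including departures (2.15.2). The CGAIS null is 4, and the alternative route is at least 80% responding (2.15.1). The candidate assessments are CGAIS, satisfaction and ease of use (1.2).

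**Assumptions.** The documents do not give the number of tests actually run or their correlation. I take 2 or 3 tests and correlations of 0, 0.5 and 0.8.

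**The plan's own figure.** One test at 0.05 has a false-positive chance of 5%, of which 2.5% is toward benefit. The plan states no error rate for the family. The sample size of 20 cannot be reproduced, because no effect size, standard deviation or power is given.

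**If any one test suffices.** With *k* independent tests:

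- Either direction: 1 − 0.95^k. For k = 2, 1 − 0.9025 = 9.75%. For k = 3, 1 − 0.857375 = 14.26%.
- Toward benefit only: 1 − 0.975^k. For k = 2, 4.94%. For k = 3, 7.31%.

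For correlated tests I use simulated normal test statistics (2 million draws, critical value 1.96):

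| Tests | Correlation | At least one significant, either direction | Multiple of 5% | At least one significant toward benefit | Multiple of 2.5% |
|---|---|---|---|---|---|
| 2 | 0 | 9.75% | 1.95 | 4.94% | 1.98 |
| 2 | 0.5 | 9.04% | 1.81 | 4.52% | 1.81 |
| 2 | 0.8 | 7.78% | 1.56 | 3.90% | 1.56 |
| 3 | 0 | 14.26% | 2.85 | 7.31% | 2.93 |
| 3 | 0.5 | 12.52% | 2.50 | 6.28% | 2.51 |
| 3 | 0.8 | 9.80% | 1.96 | 4.90% | 1.96 |

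A separate simulation with one-sample t-tests at n = 20 and correlation 0.5 gives 9.1% for two tests and 12.7% for three, so the small sample changes little.

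**If every test must be significant.** For two tests at correlation 0.5, the chance that both are falsely significant is about 0.9% in the t-test simulation. The chance that both are significant toward benefit is about 0.5%. At any correlation it cannot exceed the 2.5% of a single test.

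**The 80% route.** With 20 evaluable subjects, 80% means at least 16. The chance of reaching it is P(X ≥ 16) = Σ C(20, j) p^j (1 − p)^(20 − j), for j = 16 to 20, where p is the response rate without a true effect. At p = 0.5 this is (4845 + 1140 + 190 + 20 + 1) / 1,048,576 = 6196 / 1,048,576 = 0.6%. At p = 0.6 it is 5.1%, and at p = 0.7 it is 23.8%. These rates are assumed. Departures also change the result: with 15 evaluable subjects (at least 12 responding) the three figures are 1.8%, 9.1% and 29.7%.

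- *CGAIS.* The route adds essentially nothing under no change. With grades spread symmetrically over 3, 4 and 5, and response taken as grade 3 or better, the chance of 80% responding is at most 0.6%, and the combined rate equals that of the test alone.
- *Satisfaction.* The route can dominate. One 5% CGAIS test plus an independent 80% rule with chance s gives 1 − 0.95 × (1 − s), which is 5.6%, 9.8% or 27.6% for the three assumed rates. With the CGAIS test counted toward benefit only, 1 − 0.975 × (1 − s) gives 3.1%, 7.5% or 25.7%.

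**The case against.** The strongest reply is that the plan identifies only one fully specified test. CGAIS alone has a null. A score of 4 on the satisfaction scale means slightly satisfied, so the null of 4 does not carry over, and 2.15.5 only promises to include satisfaction in a summary. Ease of use has no instrument and no planned p-value. This stands: two or three tests is an assumption about what the rule permits, not a count in the documents.

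Second, the wording can mean that each assessment made must pass, which removes the inflation. This also stands, but it does not rescue the rule. Two readings that give opposite verdicts when the questionnaires disagree are themselves the defect.

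Third, no one would call significant worsening a success, so the two-sided column overstates false success. That is right. The fair comparison is about 4% to 7% toward benefit against 2.5% for one test. For two tests it cannot exceed 2 × 2.5% = 5%.

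A reader might infer that false success runs at a fixed 1.8 to 2.5 times a stated 5%. The documents do not support that. Those multiples need a correlation of 0.5 and leave out the 80% route. They are multiples of 5% only if worsening also counts. The 5% is not stated for this rule at all; it is borrowed from 2.15.4 and 2.15.5.

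Finally, this is a 20-subject study of a cleared device, and overall success does not depend on the secondary objectives. That limits the consequence, but the plan still attaches a success verdict to these objectives.

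**Conclusion.** The point holds as a gap in specification, with a conditional error inflation. Section 2.15.1 does not fix which assessment decides, by which route or in which direction.

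- If one of two or three tested assessments suffices at two-sided 0.05, the chance of at least one false significant result is about 8% to 14%, or 1.6 to 2.9 times 5%, for assumed correlations of 0.8 to 0. Toward benefit it is about 4% to 7% against 2.5%.
- If every assessment must be significant, there is no inflation.
- The 80% route adds an amount that the documents cannot settle.

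It would be wrong to say that the plan has no candidate for a deciding test. Section 2.15.5 names CGAIS at Visit 7 but calls it primary. Section 1.2 makes the investigator questionnaire secondary, and 3.2 says that investigator assessment of improvement, if collected, is not an objective. Nor may a reader infer that overall study success is at risk: in 2.15.1 that rests on developed parameters and an acceptable side-effect profile. The change should be made, but the study's main success criterion does not depend on it.

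**What to change.** In 2.15.1:

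1. Name one deciding efficacy test: mean Visit 7 CGAIS against 4, two-sided 0.05, with success only if the difference is toward improvement.
2. Give each assessment a single pre-set criterion in place of the either/or rule. Report the other figure alongside as descriptive.
3. Allow a satisfaction claim only if the CGAIS test succeeds, and only with a stated null or with a defined response and reference rate. Otherwise report it descriptively. The reference rate matters even in second place: 16 of 20 is passed by chance 0.6% of the time at a rate of 50%, but 23.8% at 70%.
4. Label ease of use and all other p-values as descriptive, with no success claim.

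Then reconcile the status of CGAIS across 1.2, 2.15.5 and 3.2. Editing 2.15.1 alone would leave the same variable primary in one section, secondary in another and not an objective in a third.

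With one deciding test and satisfaction gated behind it under a valid 5% criterion of its own, the family error is at most 5% two-sided. The cost is a few sentences in 2.15.1 and matching edits in the other three sections, with no new data or subjects. The downside is small: satisfaction or ease of use alone can no longer support a claim of secondary success.
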